## 5 TREATMENTS

### 5.1 Study Treatment: Abatacept

An investigational product, also known as investigational medicinal product in some regions, is defined as follows: A pharmaceutical form of an active substance or placebo being tested or used as a reference in a clinical study, including products already with a marketing authorization but used or assembled (formulated or packaged) in a way different from the authorized form, or used for an unauthorized indication, or when used to gain further information about the authorized form. In this protocol, the investigational product is abatacept.

Other medications used in the study as support or escape medication for preventative, diagnostic, or therapeutic reasons as components of a given standard of care are considered noninvestigational products.

#### 5.1.1 *Identification*

Abatacept Injection, 125 mg/Syringe (125 mg/mL), is a sterile solution for SC administration, which contains approximately 126 mg abatacept, 171 mg sucrose, 8 mg Poloxamer 188, 0.28 mg monobasic sodium phosphate, monohydrate, and 0.84 mg dibasic sodium phosphate, anhydrous, in Water for Injection. It is packaged in 1 mL long glass syringe barrel staked with a 29 gauge stainless steel needle and stoppered with a 7.1 mm rubber stopper. The composition of this solution has a ratio of monobasic sodium phosphate, monohydrate, and dibasic sodium phosphate, anhydrous, used to achieve the target pH of 7.2.

#### 5.1.2 *Storage, Handling, and Dispensing*

The investigator is responsible for ensuring that it is dispensed only to study subjects and only from official study sites by authorized personnel, as dictated by local regulations.

All investigational product supplies that will be used in the study must be maintained securely under the direct responsibility of the investigator or delegated by the investigator to the hospital pharmacist, or other personnel licensed to store and dispense drugs. All drugs shall be dispensed in accordance with the investigator's responsibility to ensure that an accurate record of drugs issued and returned is maintained.

The investigator is responsible for ensuring that the investigational product is stored under the appropriate environmental conditions (temperature, light, and humidity), as determined by the sponsor and defined by the Investigator Brochure or SmPC/ reference label. If concerns regarding the quality or appearance of the investigational product arise, do not dispense the investigational product and contact the sponsor immediately. Care should be taken when handling the injectable drug products that are used in this protocol. Proper aseptic techniques must be used when preparing and administering sterile parenteral products such as abatacept. Parenteral drug products should be inspected visually for particulate matter prior to administration. Refer to the Investigator Brochure for additional information regarding handling, preparation, and storage of abatacept.

**5.1.3        *Additional Information for the Handling, Dispensing, and Storage of Abatacept***

**ABATACEPT INJECTION FOR SUBCUTANEOUS (SC)**

**ADMINISTRATION: ABATACEPT INJECTION, 125 MG/ML, AND  
PLACEBO FOR SC ADMINISTRATION ARE READY TO USE  
SOLUTIONS PROVIDED IN PRE-FILLED SILICONIZED  
SYRINGES. NO ADDITIONAL DRUG PREPARATION IS  
REQUIRED PRIOR TO ADMINISTERING TO PATIENTS. A  
SUFFICIENT AMOUNT OF ABATACEPT OR PLACEBO  
SOLUTION IS INCORPORATED INTO EACH SYRINGE SO THAT  
EACH SYRINGE CAN DELIVER LABELED AMOUNT UPON  
ADMINISTRATION.**

**5.1.4 RECOMMENDED STORAGE AND USE CONDITIONS**

**ABATACEPT INJECTION FOR SC ADMINISTRATION: ABATACEPT SC  
FORMULATIONS (PREFILLED SYRINGES) AND CORRESPONDING  
PLACEBO SHOULD BE STORED UNDER REFRIGERATION  
(APPROXIMATELY 2°C TO 8°C). DO NOT USE BEYOND THE LABELED  
EXPIRATION DATE ON THE PRODUCT. PROTECT FROM LIGHT BY  
STORING IN THE ORIGINAL PACKAGE UNTIL TIME OF USE. DO NOT  
ALLOW THE PREFILLED SYRINGE TO FREEZE.**

**5.2        *Method of Assigning Subjects to a Treatment***

**5.3        *Selection and Timing of Dose for Each Subject***

Subjects will receive SC dose of Abatacept (125mg) or placebo at baseline for 16 weeks. Study drug will be provided for subjects to take at home. Qualified study personnel will teach subjects the proper administration of the study drug at baseline visit and teach subjects proper storage of the syringes to be taken home (see section 5.1.4 above).

**5.3.1        *Dose Modifications for Adverse Events***

If there is evidence of toxicity, as determined by laboratory tests or by clinical assessment that could place the subject at increased risk in the judgment of the investigator, administration of abatacept should be interrupted and the investigator should notify BMS. Subjects may be considered eligible to continue with abatacept treatment only if full resolution of the adverse event is documented. If the adverse event completely resolves and the next dose of abatacept cannot be

administered within 14 days of the target date, then that scheduled dose should be skipped. The next dose of abatacept should then be administered on the next targeted day for administration.

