Study Design:	Randomized trial of 32 SLE patients treated with subcutaneous abatacept 125mg sq once a week vs. 32 placebo treated subjects over a 16 week period. Patients will be seen every 4 weeks from baseline. One half of patients will be recruited at UCLA and one-half at UCSD. We expect 30 patients in each group to complete the 16 week study.
Study Schema Drugs / Doses / Length of Treatment)	Abatacept 125 mg or placebo will be administered subcutaneously once a week for 16 weeks. There will be a telephone follow up 2 months after the last injection to capture post-treatment adverse events.
Accrual Goal: (Total number of subjects)	64 (32 at UCLA and 32 at UCSD)
Accrual Rate: (Number of subjects expected per month)	2-3 subjects per month at each site
FPFV: April 1, 2015 LPFV: March 31, 2018  Follow Up: 16 weeks per patient plus 8 weeks of observation for adverse events	
Correlative Studies: These will be performed at the UCLA site only	
1) Biomarkers: a) T cell numbers and phenotypic and functional characteristic in PBMC measured at week 0 and 16. These will include for T cells CD4+, CD3+, CD25+, CD8+, Foxp3+ and cytoplasmic stains for IFNgamma, IL2, IL-17, IL21 and IL-10.
 
b) B cell numbers and subsets, including naïve, activated and plasmablasts.
 
c) Ability of autologous CD4+CD25hi T cells to suppress proliferation of CD4+CD25- T cells.
 
d) Cytokines in serum: IFNgamma, IL-6, IL-10, IL-17, IL23 and BLyS
 
2) Ultrasound with power Doppler of joints assessing synovitis, tenosynovitis (18 joints) and erosions at week 0 and 16.

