**Table 1.3.2A** **IM101063 Treatment Groups Based on Body Weight**

Treatment Group	Subject weight (kg)	IV dose on Day 1 (mg)	SC dose weekly for 12 weeks (mg)	SC injection volume (mL)
1	< 60	500	75	0.6
2	< 60	500	125	1
3	60 - 100	750	125	1
4	> 100	1000	125	1
5	> 100	1000	200	0.6 + 1.0

Source: IM101063 CSR

On Day 1, subjects received a single IV infusion (loading dose) of abatacept or placebo, based on their weight range. Approximately 1 hour after the completion of the IV infusion, subjects received their assigned SC dose of abatacept or placebo. Abatacept or placebo was administered weekly by the SC route, at the same dose as the SC dose on Day 1, for a total of 12 SC injections. Blood samples for PK analysis were collected on Day 1 prior to and at the end of the IV infusion. In addition, blood samples were collected prior to each weekly SC dose of abatacept.

Steady-state trough serum concentrations were achieved after ~ 4 to 5 weeks following the combined regimen of a single IV loading dose and weekly SC injections. With the exception of Treatment group 4 (abatacept 125 mg SC weekly dose for subjects weighing > 100 kg), the mean steady-state trough concentrations across all other treatment groups appeared to be comparable.

However, to truly represent the steady-state serum levels from SC administration without the contribution of the IV loading dose, Cmin values on Days 71-85 were selected, since contribution from IV was expected to be negligible. Comparison of mean steady-state trough concentrations on Day 71, 78 and 85 indicated that abatacept did not appear to accumulate following weekly dosing (Table 1.3.2B).

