### **3.4 Stopping Rules**

The study will be put on hold if 1) there are two deaths thought to be possibly, probably or definitely related to the treatment, or 2) there are 3 patients with SAEs thought to be probably or definitely related to the treatment. If either of these occurs, the study will be suspended until the DSMB determines whether it is safe for patients to continue on the therapy. This determination will be made within two weeks of the events described so that patients will hold their doses of abatacept or placebo for no longer than two weeks if the reviewers determine it is safe to continue. A data safety monitoring board (one to-be-named Rheumatology faculty member plus one to-be-named statistician) will review the SAEs quarterly and issue a report to the IRB and to the investigators regarding AEs and SAEs, reported according to patient assignments to groups A or B (the double-blind code will not be broken); these reports will also be supplied to the sponsor

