## **4            INVESTIGATIONAL PLAN**

### **4.1            Study Design and Duration**

This is a randomized placebo-controlled double-blind study for the 16 weeks, in patients with SLE whose active lupus manifestation is primarily arthritis. The study consists of a baseline visit, a 16-week treatment period (with visits every 4 weeks), and a telephone follow up 8 weeks after the last dose of study drug. Patients are expected to participate in the study for up to approximately 26 weeks (including screening visit).

Informed consent will be obtained at the Screening Visit, prior to patients undergoing any study procedures. Eligibility criteria will be assessed and medical history will be reviewed prior to Protocol Amendment 1, November 30, 2015

patient's participation in this study. Starting at the baseline visit, patients will receive 125 mg sc of abatacept or placebo every week for 16 weeks. Patients may continue on their stable background standard of care medications (according to the protocol) throughout the study. In the first dose visit, patients will be monitored for systemic symptoms for at least 1 hour after abatacept has been administered.

Subjects who discontinue the trial early, i.e. prior to Week 16 should come to a follow-up study completion visit within 1 week of treatment termination.

Unscheduled visits for safety or for any other reason may be conducted at any time during the study.

During the study period, at 4 week intervals, swollen and tender joint counts (28 joints), the British Isles Lupus Assessment Group (BILAG) score, SLE Disease Activity Index (SLEDAI 2K), Physician Global Assessment Score and Patient Global Assessment will be assessed in addition to routine safety laboratory and physical tests. Disease related immunology tests/biomarkers will be taken at baseline and 16 weeks.

Bilateral Posterior-Anterior (PA) Hand X-rays (including wrists) will be performed at baseline for all subjects. Ultrasound examination of the PIP (2-5), MCP (2-5), and wrist joints designated below will be performed at baseline and at 16 weeks. At baseline and 16 weeks, synovitis (18 joints), tenosynovitis and erosions will be assessed.

Please see Time and Events Schedule in Section 6.

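### The 14-day late-dose window in section 5.3.1 is twice the 7-day dosing interval, and the protocol does not say how a late dose relates to the dose then due

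*Combined protocol and SAP*

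**What the plan says.** **Schedule.** The Protocol Synopsis states: "Abatacept 125 mg or placebo will be administered subcutaneously once a week for 16 weeks". Section 4.1 agrees: "Starting at the baseline visit, patients will receive 125 mg sc of abatacept or placebo every week for 16 weeks". After the first dose at the site, patients inject at home (5.3, 5.6). Drug is dispensed at baseline and at Visits 2 to 4, which are four weeks apart (6.1).

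**Late-dose rule.** Section 5.3.1 has dosing interrupted for toxicity, with notice to the company supplying the drug. Treatment may continue only once full resolution is documented. If the event resolves but the next dose cannot be "administered within 14 days of the target date, then that scheduled dose should be skipped. The" (the last word opens the following sentence). That sentence reads in full: "The next dose of abatacept should then be administered on the next targeted day for administration". Target days therefore stay fixed; the calendar does not shift with the restart.

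**Other holds.** Under section 3.4 the whole study can be suspended for safety review, in which case "patients will hold their doses of abatacept or placebo for no longer than two weeks if the reviewers determine it is safe to continue". Section 5.6 withholds drug during a significant infection until it has clinically resolved. Neither section says how missed doses are treated at restart.

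**Silence elsewhere.** Sections 5.3, 5.6 and 5.7 set no minimum gap between doses and no limit on doses per day. They do not say that a late dose takes the place of the one then due. Section 5.7 asks only for a weekly dosing diary and drug reconciliation.

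**The concern.** A late-dose window separates a dose that is merely late from one that is lost. It can do that only if it is shorter than the dosing interval. Here it is twice the interval, so by the time a held dose is 7 days late the next dose has fallen due and the first has not been skipped. Section 5.3.1 then leaves three questions open:

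- Does the late dose replace the dose now due, or add to it?
- What happens to any other dose that fell due during the interruption?
- Does day 14 itself count as inside the window?

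The rule applies to patients restarting after toxicity, who inject themselves at home and may hold several dispensed syringes. Two investigators could follow the same paragraph and give different exposure. One of the available readings departs from the once-weekly regimen that the trial is testing.

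**Working it through.** The 14 days is a stated rule, not a derived figure, so there is nothing to reproduce. The check is a direct count.

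**Inputs**
- Dose 125 mg, interval 7 days (Synopsis; 4.1)
- Window 14 days from the target date of the dose (5.3.1)
- Target days fixed, with resumption on the next one after a skip (5.3.1)

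**Step 1. Window against interval.** 14 / 7 = 2 intervals.

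**Step 2. Doses not ruled out on the restart day.** Let t be the number of days from the target date of the first held dose to the restart. Targets fall at d = 0, 7, 14, and so on. A dose is due and not skipped if d ≤ t and t − d ≤ 14 (or < 14 if day 14 is outside the window). The counts assume that no dose replaces another, because the text does not say that one does. The last column is a narrower reading: only the first held dose may be given late (day 14 inside), together with any dose due on the restart day itself.

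| Restart day t | Window for each dose, day 14 inside | Window for each dose, day 14 outside | Only the first held dose may be late |
|---|---|---|---|
| 0 to 6 | 1 (125 mg) | 1 (125 mg) | 1 (125 mg) |
| 7 | 2 (250 mg) | 2 (250 mg) | 2 (250 mg) |
| 8 to 13 | 2 (250 mg) | 2 (250 mg) | 1 (125 mg) |
| 14 | 3 (375 mg) | 2 (250 mg) | 2 (250 mg) |
| 15 to 20 | 2 (250 mg) | 2 (250 mg) | 0, wait for day 21 |
| 21 | 3 (375 mg) | 2 (250 mg) | 1 (125 mg) |

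Two doses on one day are reached in all three columns. Three are reached only in the first, and only when the restart falls on a target day at t = 14 or later.

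**Step 3. Worked case.** The dose due on day 28 is held and dosing restarts on day 42.
- Day-28 dose: 42 − 28 = 14 days late
- Day-35 dose: 42 − 35 = 7 days late
- Day-42 dose: 0 days late

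With the window applied to each dose and day 14 inside, none is skipped: 3 × 125 = 375 mg. With day 14 outside, the day-28 dose is skipped: 2 × 125 = 250 mg. If a single dose is given in place of all three, 125 mg.

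**Step 4. Exposure over the trial.** Weekly dosing for 16 weeks is 16 doses. In the worked case a patient receives 16 of 16 if both held doses are made up, or 14 of 16 (87.5%) if neither is.

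**Step 5. The other holds.** A 3.4 hold of two weeks is also 14 / 7 = 2 dosing intervals, and a 5.6 hold has no stated length. Both can therefore span scheduled doses, and neither section refers to 5.3.1.

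**The case against.** The strongest reply is that same-day multiples are inferred, not written. Section 5.3.1 says when a dose is skipped. It does not say that every dose inside 14 days must be given, still less given on top of the dose then due. It speaks of the next dose in the singular. Read with the once-weekly schedule and the weekly diary, a sensible investigator would not double up. Restart also needs documented resolution, so it is not left to the patient. This stands as far as it goes: the text permits multiples and does not order them. It does not remove the mismatch, because the investigator must set the schedule against 5.3.1 to reach that answer, and 5.3.1 does not supply it.

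Several stronger readings are tempting and the documents do not support them.

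- **That the rule leads to 375 mg on one day.** This needs all three conditions in step 2 and is the extreme case.
- **That this exceeds anything in the protocol's data.** The largest weekly subcutaneous dose in Table 1.3.2A is 200 mg. But in that study the Day 1 dose was given about an hour after an intravenous load, for 575 mg (500 + 75) to 1200 mg (1000 + 200) in one day. The route differs, so this neither clears nor condemns 375 mg.
- **That a patient following the rule would have a reportable overdose.** Section 7.5 requires a dose judged both excessive and medically important, and nothing in the documents establishes that here.
- **That a 3.4 hold would put every patient on treatment in the same position.** Section 5.3.1 concerns an individual's adverse event and is not stated to govern a study-wide hold. What can be said is that 3.4 has no late-dose rule of its own.
- **That the resume clause cannot work because the next target day has always passed.** Whether a dose can be given in time may be judged in advance, and a later target day exists until treatment ends.

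**Conclusion.** The point holds as an internal inconsistency. A 14-day window does not fit a 7-day schedule, and no other section says how a late dose relates to the dose then due. With fixed target days and no replacement rule, the wording permits two doses (250 mg) on one day. Three (375 mg) is possible only under the conditions in step 2. The mismatch itself is certain; same-day multiples depend on how a site reads silence.

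The documents give no frequency of interruptions, so the number of patients affected cannot be estimated, and differing practice between the two sites is a possibility rather than a finding. Sample size, error rates and the primary analysis do not depend on the point. It matters for patient safety after an adverse event and for consistent exposure, and it is cheap to settle.

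**What to change.** The sponsor and the investigator should reconcile the 14-day window in section 5.3.1 with the weekly schedule in the Synopsis and section 4.1. The reconciled text should make explicit how a late dose relates to the dose then due, how other doses falling due during the interruption are treated, and whether day 14 is inside the window. It should also state whether it covers the holds in sections 3.4 and 5.6. The clinical content is theirs to decide; no dose, window or rule is proposed here.

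The cost is one paragraph in a protocol amendment and a matching line in the dosing diary instructions. No visits, patients or analyses are added.

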#### **5.4 Blinding/Unblinding**

No data will be unblinded until the conclusion of the study, unless a serious adverse event cannot be treated effectively without the information, or unless 2 or more deaths that may be related to the therapy occur.

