### **STUDY IN SYSTEMIC LUPUS ERYTHEMATOSUS**

In NCT 001 10678, A phase IIb study in SLE was conducted and published. 118 patients were treated with 10mg/kg abatacept i.v. in the standard RA dose, and 57 with placebo. 65% completed 12 months of study. The primary outcome, rate of flare beginning after prednisone taper, over a total of 12 months, measured by adjudicated BILAG A and B, did not show significant differences between the groups. However, patients with lupus polyarthritis at entry had significantly fewer flares compared to placebo in both BILAG A flare (36.5% in placebo vs 12.5% in abatacept) and physician-identified flares. The incidence of serious adverse events was higher in abatacept (19.8%) vs placebo (6.8%) without any particular type of SAE identified.

In a recent study in patients with lupus nephritis, 198 individuals were treated with abatacept i.v.. for 12 months (one group with a loading dose of 30 mg/kg once a month x3 followed by 10 mg/kg monthly; a second with 10 mg/kg monthly i.v. for the entire 12 month period). At 12 months, there were no statistically significant differences in response rates (defined as complete renal response or partial- plus- complete renal responses) between the group that received placebo infusions plus standard care compared to either of the groups that received abatacept plus standard care. The occurrence of severe adverse events did not differ significantly between the groups: SAEs occurred in 28-33.3% of the abatacept groups and 31% of the placebo group. There were 7 deaths in the abatacept groups (one of which was a gunshot wound) for a rate of 2.5%, with 7 deaths in the placebo group for a rate of 7%. Treatment related SAEs occurred in 19-20% of the abatacept groups and 15% of the placebo groups.

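### Section 5.4 has no unblinding exception to match the 3-patient SAE hold in 3.4, so the DSMB would decide on continuation without a route to learn which coded group is abatacept

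*Combined protocol and SAP*

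**What the plan says.** **Section 3.4 (Stopping Rules)** sets two hold triggers:

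- "there are two deaths thought to be possibly, probably or definitely related to the treatment"; or
- "there are 3 patients with SAEs thought to be probably or definitely related to the treatment".

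The SAE trigger is a pooled count over both arms. The consequence is the same for both triggers: "the study will be suspended until the DSMB determines whether it is safe for patients to continue on the therapy". A time limit follows: "This determination will be made within two weeks of the events described".

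**Section 5.4 (Blinding/Unblinding)** sets the general rule and its first exception: "No data will be unblinded until the conclusion of the study, unless a serious adverse event cannot be treated effectively without the information". The second exception is "unless 2 or more deaths that may be related to the therapy occur". There is no third.

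**Sections 3.4, 6.3 and 7.3** carry the same sentence on the board's quarterly review. The board reports AEs and SAEs to the IRB and the investigators, with copies to the sponsor, "reported according to patient assignments to groups A or B (the double-blind code will not be broken").

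**The concern.** The two hold triggers lead to the same question, but only one has a matching exception to the blind. By allowing unblinding after two possibly related deaths, the plan accepts that treatment identity may be needed at a hold. It then leaves out the SAE trigger.

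The board's question is about the therapy. Coded counts show how unevenly events fall, but not on which side. A 3-0 split against abatacept and a 3-0 split against placebo look the same, yet they bear differently on whether dosing should resume.

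Direction is a fair question in this disease. For the 12-month non-nephritis SLE trial of IV abatacept, the protocol reports SAEs in 19.8% on abatacept and 6.8% on placebo, and Section 1.3.4 treats those patients as the most comparable to the ones planned here. The evidence is not all one way: in the nephritis trial SAEs did not differ significantly (28-33.3% on abatacept, 31% on placebo).

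There is a second, smaller gap. The death exception lifts the blind on data without saying for whom. Read literally, it could unblind investigators and the sponsor during the trial.

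**Working it through.** **1. The sections side by side**

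| Event | Hold under 3.4? | DSMB decision within two weeks? | Exception in 5.4? |
|---|---|---|---|
| 2 deaths, at least possibly related | yes | yes | yes, recipient not stated |
| 3 patients with probably or definitely related SAEs | yes | yes | none |
| One SAE that cannot be treated without the code | no | no | yes, tied to treating that event |

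The third row might reveal one affected patient's arm by chance, but gives the board no general access. The A/B sentence in 3.4, 6.3 and 7.3 governs the quarterly reports the board issues. It does not say what the board may receive at a hold. The bar on access is therefore the general rule in 5.4, together with the absence of any text that grants it.

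**2. What the coded split can show**

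The planned arms are 32 and 32 (synopsis; 8.1). Suppose three of the 64 patients are affected and treatment has no effect:

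- P(3-0 either way) = 2 × C(32,3) / C(64,3) = 2 × 4,960 / 41,664 = 0.24
- P(2-1 either way) = 1 − 0.24 = 0.76

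Fisher's exact two-sided p is 0.24 for 3/32 v 0/32 and 1.0 for 2/32 v 1/32. Three events are weak evidence on their own. Knowing the direction adds something, mainly at 3-0, but does not settle the question.

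**3. How often the SAE trigger would fire**

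The plan states no figure, so there is none to reproduce. Let X be the number of patients with a qualifying SAE, as the sum of two independent binomials with n = 32 each. The trigger fires when X ≥ 3. With one common rate p:

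P(X ≥ 3) = 1 − (1−p)^64 − 64p(1−p)^63 − 2016p²(1−p)^62

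- p = 1% (assumption): 1 − 0.5256 − 0.3398 − 0.1081 = **0.027**
- p = 2%: 1 − 0.2745 − 0.3585 − 0.2304 = **0.137**. The 2% comes from the 4-month SC study in RA (IM101173), where 2 of 100 subjects had SAEs at least possibly related.
- Nephritis trial: treatment-related SAEs over 12 months in 19-20% on abatacept (19.5% taken) and 15% on placebo.
  - Linear scaling, × 16/52: 6.0% and 4.6%; expected number 32 × 0.060 + 32 × 0.0462 = 3.40; P = **0.67**
  - Constant hazard, 1 − (1−p)^(16/52): 6.46% and 4.88%; expected number 3.63; P = **0.71**
  - If only half of those constant-hazard events qualified (3.23% and 2.44%): P = **0.27**

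**4. Why these rates are proxies**

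The trigger needs a probable or definite relation. The 2% counts possible relations as well, so 14% is not a lower bound. The nephritis figures use a treatment-related category that the protocol does not equate with probable or definite, from IV dosing in patients with nephritis, a condition this trial excludes when active. Section 7.2 also grades causality only as related or not related, so the documents do not say how the three-level wording in 3.4 would be applied when counting.

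**The case against.** The strongest reply is that the board is not helpless. Nothing stops it from reviewing event type, severity, timing, case causality and the A/B split. It can treat an imbalance as if it were on active drug, or ask for the code by amendment. With three events, case-level judgement may matter more than the arm count. All of this stands.

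A reader might therefore infer one of three stronger claims. The documents do not support them:

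- *That the decision cannot be made, or that the board must either stop a blameless drug or restart a harmful one.* The board keeps real information and intermediate options. What it lacks is one relevant fact.
- *That the trigger signals an excess in one arm.* It is a pooled count. With no treatment effect, about three in four such holds would be a 2-1 split.
- *That the wording about not breaking the code should be deleted.* It protects the blind of those who receive the board's reports, and should stay.

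It can also be said that masking a safety board is a legitimate choice. It is, but this plan does not make that choice consistently, since it permits unblinding at one of its two holds. A separate board charter could settle the matter; the documents cite none.

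**Conclusion.** The mismatch is in the text and does not depend on any rate. The death trigger has an unblinding exception, the SAE trigger has none, and no section gives the DSMB the A/B key. At an SAE hold the plan, followed as written, withholds the direction of any imbalance from the people asked to judge safety. The open-ended recipient of the death exception is a lesser gap in the same section.

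How often this would matter is uncertain: about 3% at an assumed 1% per arm, 14% at 2% per arm, and up to about 70% with the nephritis trial's broader rates, which likely overstate it. All of these assume 32 patients per arm and independent events, and the last also needs 12-month rates scaled to 16 weeks. A reader might take the upper end to mean that a hold is likely. The inputs are too broad for that.

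This is worth an amendment because it bears on a safety decision and is cheap to settle. It is not a flaw that makes the stopping rule unworkable.

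**What to change.** Reconcile 3.4 and 5.4 with one rule stated in both places:

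- On either hold trigger, the identity of groups A and B may be released, on request, to the DSMB members only, in closed session.
- Investigators, assessors, patients and the sponsor stay blinded. This also gives the death exception a defined recipient.
- The amendment says who releases the key and how the release is recorded.

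Keep the A/B coding and the unbroken-code wording for the reports the board issues to the IRB, investigators and sponsor. Because those reports are coded by group, one patient's revealed assignment could identify both groups to their readers, which is a further reason for a DSMB-only route.

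The cost is a few sentences, with no added patients, visits or assessments and no change to the triggers. The downside is that the two DSMB members could know the key before database lock. The documents describe them only as a rheumatology faculty member and a statistician, both still to be named, so the amendment should also require that they be independent of the trial team.
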